### 2) Secondary Outcome Measure Analysis

Outcome Measures: Using the FAS as the analysis population, comparisons of the mean change in JESS, nocturnal sleep assessments (AHI, ODI, nocturnal hypoxia, arousal status, etc.), and Japanese CAT scores between groups will be tested at a 5% significance level. A similar analysis will be performed secondarily using PPS as the analysis population.

Safety Assessment: Not applicable

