### First Intervention Session (within one month of participant enrollment):

- 1) During a video conference, the participant will be asked to use their prescribed inhaled medication while the study staff (applicant) observes their inhalation technique. The staff will assess the technique using a standardized technical checklist. Feedback will be provided based on the assessment, and any technical errors will be corrected through demonstration of the correct inhalation method.

- 2) Education will be provided on self-management, including how to use inhaled medications in response to symptoms such as dyspnea and cough perceived in daily life, appropriate timing of inhalation, and self-monitoring strategies.

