### At the time of enrollment

[Patient Basic Information]

Patient Background: Age, Gender, Smoking History, BMI, Disease Duration, Alcohol Consumption (presence/absence and frequency), Use of Sleep Medications, Hospitalization within the Past 6 Months, Presence of Comorbidities (e.g., Diabetes, Heart Disease, Stroke, Hypertension, Depression, Cognitive Impairment), mMRC, Types and Number of Inhaled Medications

Respiratory Function: FVC (ml), FEV1 (ml), FEV1/FVC (%), %FEV1 (%) measured between 6 months prior to enrollment and the first intervention

Sleep assessment: AHI, ODI, snoring level, wakefulness/sleep depth, REM sleep structure, oxygen saturation (mean minimum oxygen saturation, frequency of oxygen saturation drops, heart rate during sleep) using Watch Pad 200U or 300

Inhalation therapy experience: Presence/absence of inhalation therapy instruction and details (providing profession, time since last instruction, past instruction method [demonstration, video, pamphlet, verbal])

[Self-Administered Questionnaire I]

Anxiety/Depression Tendencies: Japanese Version of the Hospital Anxiety and Depression Scale (HADS)

QOL: Japanese Version of the CAT

Sleep Quality: PSQI-J, JESS

Initial Intervention: Within one month of participant registration

Inhalation Technique: Assessment using the Inhalation Technique Checklist

- Presence of technical errors

Second Intervention: Approximately 4 weeks after initial intervention

Inhalation Technique: Assessment using Inhalation Technique Checklist

- Presence of technical errors
- Changes to device, medication content, or frequency and reasons

[Self-Report Questionnaire II]

Sleep Quality: PSQI-J, JESS

Anxiety/Depression Tendencies: HADS

Study Completion (Approximately 8 weeks after second intervention)

Inhalation Technique: Assessment using Inhalation Technique Checklist

- Presence of technical errors
- Changes in device, medication type, or dosage frequency and their reasons

Sleep Assessment: AHI, ODI, snoring level, arousal/sleep depth, body position, REM sleep structure, oxygen saturation statistics (mean minimum oxygen saturation, frequency of oxygen saturation drops, heart rate during sleep) using Watch Pad 200U or 300

[Self-Report Questionnaire III]

Sleep Quality: PSQI-J, JESS

QOL: Japanese CAT

Anxiety/Depression Tendencies: HADS

Presence of unscheduled visits or hospitalizations from enrollment to study completion

[Brochure]

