Self-assessment of inhaler usage, inhalation log (symptoms of breathlessness, cough/phlegm, self-rated sleep)

Table1. Inspection Schedule

	within 6weeks	registration	Initial intervention	Second intervention	At the completion of the research	Cancellation
Pulmonary Function Test	○					
Patient Basic Attributes		○				
QOL (Quality of life)		○		○	○	△
PSQI · JESS (Sleep quality)		○		○	○	△
Sleep Assessment (Sleep study)		○			○	△
Check of inhalation technique		○※	○※	○	○	△
HADS (Anxiety and Depressive Tendencies)		○		○	○	△
Unplanned medical visits or hospitalizations					○	△
Observation of adverse events			◀	▶		△
Inhalation Management Log					○	△

“○” indicates required items; “△” indicates optional items;

“※” indicates items to be completed during registration or around the time of the first intervention.

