## 10. Analysis Methods

### 1) Analysis of Primary Endpoint

#### Primary Endpoint: PSQI-J at 3 months post-educational intervention

Analysis of the primary endpoint will be performed using the Full Analysis Set (FAS). The change in PSQI-J for each group will be calculated, and between-group comparisons will be performed at a 5% significance level (two-tailed) using covariance analysis adjusted for the background factors of age and disease stage classification. A similar analysis will be performed secondarily using PPS as the analysis population.

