## **12. Informed Consent Documents and Methods for Obtaining Subject Consent**

The Principal Investigator or Co-Investigator shall provide the research subject with the informed consent document approved by the Kumamoto University Clinical Research Ethics Review Committee (hereinafter referred to as the Ethics Review Committee) and authorized by the head of the research institution. They shall provide a thorough explanation both verbally and in writing and obtain the research subject's written informed consent freely given. Furthermore, when information regarding efficacy, safety, or other factors that could influence the research subject's consent is obtained, or when changes to the implementation plan or other aspects that could affect the research subject's consent are made, the research team shall promptly provide this information to the research subject. The research team shall confirm the research subject's intention regarding participation in the research in advance. The research team shall also revise the explanatory document, etc., after obtaining prior approval from the Ethics Review Committee and permission from the head of the research institution, and obtain renewed consent from the research subject.

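### Section 10 declares safety assessment not applicable although Table 1 schedules adverse-event observation, and no summary by arm is planned for adverse events or for unplanned visits and hospitalisations

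*Protocol*

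**What the plan says.** Section 10, item 2, sets out the secondary analysis as "comparisons of the mean change in JESS, nocturnal sleep assessments (AHI, ODI, nocturnal hypoxia, arousal status, etc.), and Japanese CAT scores between groups", and closes with "Safety Assessment: Not applicable". Section 10, item 1, covers only the primary endpoint, given as "Primary Endpoint: PSQI-J at 3 months post-educational intervention".

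Section 9 collects more than this. Table 1 has a row headed "Observation of adverse events" and a separate row headed "Unplanned medical visits or hospitalizations". The second is marked as required at completion and optional at cancellation. The list of items at study completion also includes "Presence of unscheduled visits or hospitalizations from enrollment to study completion".

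Two other places bear on the point. The first session in Section 7 includes teaching on "how to use inhaled medications in response to symptoms such as dyspnea and cough perceived in daily life". Section 12 requires participants to be informed promptly "when information regarding efficacy, safety, or other factors that could influence the research subject's consent is obtained".

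**The concern.** A protocol that said nothing about adverse-event tables would give no cause for comment, because that detail usually belongs in the statistical analysis plan. This protocol does say something: it schedules adverse-event observation in one section and declares safety assessment inapplicable in the next. An analysis plan that tabulated adverse events would depart from the protocol, and one that followed the protocol would leave the collected data without a summary.

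What is at stake is the harms side of the report. The intervention goes beyond demonstrating inhaler technique. It covers when and how participants use active drugs in response to symptoms. Section I also links poor sleep in COPD to exacerbation risk, so unplanned visits and admissions are informative about benefit as well as harm. A reader of the results would expect to see these events by group.

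**Working it through.** The point rests on no figure in the protocol, so the check is a comparison of the text.

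1. **What is collected.** Table 1 gives adverse events a row of their own. Unplanned visits and hospitalisations have a second row, and the study-completion list in Section 9 gives their period as enrolment to completion.

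2. **What is named as an outcome.** Section 8 names PSQI-J as primary. The secondary items are JESS, the overnight sleep measures, CAT and inhalation technique errors. Neither adverse events nor unplanned visits and hospitalisations are among them.

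3. **What is analysed.** Section 10 plans comparisons of PSQI-J, JESS, the overnight sleep measures and CAT. Of the two event items in step 1, none enters a planned comparison or summary.

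4. **What is said about safety.** The only statement in the analysis section is "Safety Assessment: Not applicable". Elsewhere, Section 12 expects that safety information may arise during the study.

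5. **How the two items differ.** The adverse-event row conflicts with an explicit statement. The unplanned-visit row does not: the protocol never labels those data as safety data, and Section 10 merely omits them. HADS is likewise collected but unlisted in Section 10, and inhalation technique errors are a named secondary item that Section 10 also leaves out. For unplanned visits and hospitalisations, the accurate statement is therefore that no summary by arm is planned, not that one is ruled out.

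**The case against.** The strongest defence is that the line stands under the secondary outcome analysis and means only that there is no safety endpoint to test. That agrees with Section 8, and watching for adverse events to protect participants is compatible with having no safety endpoint. The intervention is education about inhalers already prescribed, and the protocol documents no event rate or mechanism of harm. Part of this stands: the line can be read that way, and an imbalance between arms is a possibility, not something the documents show. But the protocol does not give that reading, and even under it the adverse-event row has no stated use in the results.

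Three stronger readings are tempting and should not be taken.

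- **That harms will never be compared.** Nothing in the protocol forbids a descriptive table, and an analysis plan that is not shown could contain one. What can be said is that the protocol plans none.
- **That adverse events are watched only between the two sessions.** In the readable text the arrowheads fall in those two columns, but they may be the ends of one longer arrow whose span was lost when the table was read. They are not evidence of a shortened window.
- **That controls have no adverse-event window.** Table 1 is not split by arm, and Sections 6 and 14 give controls a technique check by video. How the visit columns apply to controls is a separate question about the schedule.

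Nor does the small size of the arms measure this defect. The limited precision for rare events would be the same with the proposed table.

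**Conclusion.** The point holds in a limited form. Section 10 and Table 1 disagree on adverse events, and the protocol plans no summary by arm of either adverse events or unplanned visits and hospitalisations. The conflict is firm for adverse events because it rests on two explicit entries. For unplanned visits and hospitalisations there is only an omission, which is best repaired in the same sentence.

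Its reach is confined to harms reporting: the primary comparison, the listed secondary comparisons and the sample size are untouched. It is still worth correcting before analysis, since the data are to be collected anyway and the education bears on how inhaled drugs are used. The conclusion assumes that the adverse-event row in Table 1 reflects real data collection. It does not depend on where the arrows fall, or on any assumed event rate.

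**What to change.** Reconcile Section 10 with Table 1. Replace the not-applicable line with a statement such as: adverse events, and unscheduled visits or hospitalisations, will be tabulated by allocated group for all allocated participants, giving the number of participants affected and the number of events, without a formal test. State one observation window that applies equally to both arms.

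The sponsor should compare the adverse-event row with its own copy of Table 1. If that copy already covers the stated window for both arms, the row needs no change; otherwise it should be aligned.

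The cost is one sentence, possibly one table row, and one descriptive table, drawn largely from data the protocol already collects. No added visit, larger sample or change to any planned test is needed.

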##### Rationale for Sample Size:

There are no previous studies that have specifically examined the impact of inhalation management education on sleep quality. In prior studies, the mean PSQI (Pittsburgh Sleep Quality Index) scores among patients with COPD ranged from 8.3 to 11.5, with a commonly used cutoff score of 5.5 to indicate poor sleep quality. Based on this, we assumed a mean reduction of 5.0 points in the PSQI-J score at 3 months in the intervention group.

Using a two-tailed test with a significance level of 5% ( $\alpha = 0.05$ ) and a power of 80% ( $\beta = 0.20$ ), the required sample size was calculated to be 17 participants per group.

[figure not shown]
However, considering that many participants are older adults who may face challenges in consistently using personal computers or video conferencing tools, a higher dropout rate than usual is expected. Therefore, we increased the target enrollment to 30 participants per group, for a total of 60 participants.

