## 7. Intervention

The intervention content for the education intervention group is described below. The usual care group will receive only the same pamphlet as the intervention group, without any explanation or instruction on inhalation techniques.

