**Second Intervention Session (four weeks after the first session):**

- 1) During a video conference, the participant will again demonstrate inhalation using their prescribed inhaler, observed by the study staff who will assess technique with the checklist. Feedback will be given, and any technical errors will be addressed through correct method demonstration.
- 2) The staff will inquire about any difficulties or symptoms experienced by the participant since the previous intervention, and discuss inhaler use and management strategies together with the participant.

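### Adverse events are scheduled but have no summary by group, and unscheduled care need not be recorded for participants who stop early

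*Protocol*

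**What the plan says.** Three places in the protocol bear on this.

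- **Schedule (section III.9, Table 1).** There is a row for "Observation of adverse events", drawn as a span with an entry in the cancellation column, and a row for "Unplanned medical visits or hospitalizations", marked as required at completion with an entry at cancellation. The cancellation entries are triangles, and the legend says that a triangle "indicates optional items". The list of items at study completion in the same section includes "Presence of unscheduled visits or hospitalizations from enrollment to study completion".
- **Analysis (section III.10, part 2).** After the secondary outcomes to be compared, the text states "Safety Assessment: Not applicable".
- **Expected losses (section III.5, rationale).** Because many participants are older and may struggle with video conferencing, "a higher dropout rate than usual is expected". No rate is given.

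Section III.8, which defines the primary and secondary evaluation items, names neither adverse events nor unscheduled care.

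**The concern.** The schedule commits the sites to observing adverse events, and the analysis section then makes an explicit statement that safety is not assessed. A study team following both would hold adverse-event data with no stated use by group, and could properly report none.

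The intervention is educational and low-risk, but it is not inert. Section III.7 has staff correct inhaler technique and teach how and when to use inhaled medication in response to symptoms. It can therefore change how patients use their drugs. Unscheduled visits and hospitalisations are clinically relevant in COPD and are already being collected.

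The second gap is in who contributes data. Those who leave early may differ from those who finish. If unscheduled care has to be recorded only for finishers, any later tally by group describes finishers rather than everyone randomised. What is at stake is harm reporting, not the efficacy result.

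**Working it through.** The protocol gives no figure to reproduce here, so the check is a comparison of the texts.

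**Step 1. Adverse events: schedule against analysis.**

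| | Table 1 (III.9) | Analysis (III.10) |
|---|---|---|
| Adverse events | Scheduled as a span; optional at cancellation | Safety assessment declared not applicable |
| Unscheduled visits or hospitalisations | Required at completion; optional at cancellation | Not mentioned |

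For adverse events, a scheduled item meets an explicit statement against assessing it. For unscheduled care the analysis section is only silent, which by itself is not a contradiction and could be left to an analysis plan.

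**Step 2. What is required for a participant who stops early.**

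- Unscheduled care: the only required entry is at completion, which this participant does not reach. The cancellation entry is optional. Required records: none.
- Adverse events: the row is a span, so events within it should be noted as they arise. Only the entry at cancellation is optional. The gap is weaker here.

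**Step 3. How many participants this could touch.** No dropout rate is stated. The only related figures are the calculated requirement of 17 per group and the target of 30 per group in the sample-size rationale. If the whole increase is read as an allowance for dropout, which is an assumption, then:

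- 30 − 17 = 13 per group
- 13 / 30 = 0.43

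On that assumption, between 0 and 13 of 30 participants per group would have no required record of unscheduled care. This counts participants, not events. With no event rate in the protocol, the number of missed events cannot be derived.

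**Step 4. Effect on the primary analysis.** The PSQI-J comparison (III.10, part 1) uses neither item, so its estimate and test do not change.

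**The case against.** The strongest reply is that the line in III.10 sits among outcome analyses and follows the list of outcomes to be tested, while III.8 names no safety endpoint. It may mean only that no safety outcome is tested. Observing adverse events for participants' protection, and passing on safety information that could affect consent (III.12), both fit that reading. Tabulation could be left to an analysis plan. This softens the point but does not remove it: if that is the meaning, the line should say so, because a plan that tabulated adverse events would have to depart from the protocol's wording.

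It is also fair that the triangle at cancellation is a general convention. Every row with a cancellation entry carries it, including the PSQI row, so harm data were not singled out. Section III.9 also allows retrieval from medical records with permission. Both facts stand, but nothing requires that retrieval for a participant who stops.

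A reader might go further in three ways that the documents do not support.

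- **A short observation window.** In the extracted table the adverse-event arrows appear to run only from the first to the second session. Their position may be an artefact of reading the PDF and cannot carry a conclusion.
- **Symptoms asked about in one arm only.** At the second education session, "The staff will inquire about any difficulties or symptoms experienced by the participant since the previous intervention", while "The usual care group will receive only the same pamphlet as the intervention group". But that enquiry is educational content, not described as adverse-event ascertainment. Control participants also have staff contact by video for a technique check (III.6), with calls of about 30 minutes (III.14, part 3), and unscheduled care is collected at completion without restriction to one group.
- **A measured loss from poor precision.** Confidence limits for a table of about 30 per group would describe the proposed table, not any damage done by the present text.

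**Conclusion.** The point holds in a limited form and is minor. Adverse-event observation is scheduled, while the analysis section declares safety assessment not applicable, so as written the data have no summary by group. Unscheduled visits and hospitalisations have no required record for participants who stop early, in a trial that expects more stopping than usual.

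The number of events affected cannot be estimated and may be zero if records are retrieved. The conclusion assumes that the triangle is applied as the legend defines it, and that the analysis line is followed as worded. It does not support a claim that the protocol ignores participants' safety, or that the PSQI-J result is compromised.

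**What to change.** In section III.10, part 2, replace "Safety Assessment: Not applicable" with text such as:

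*No safety endpoint is tested. The number and percentage of randomised participants with at least one adverse event, and with at least one unscheduled visit or hospitalisation, will be tabulated by allocated group, with the number without a record in each group.*

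In Table 1, change the cancellation entry from optional to required for unscheduled visits or hospitalisations and for any adverse events to date. The information can come from interview or, where the participant's permission stands, from medical records, as III.9 already allows.

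The cost is one replaced line, two symbols, and a short interview or record check for each participant who stops. No new visit or test is needed. At about 30 per group the percentages will be imprecise and should be presented as descriptive only.

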## **11. Study Period**

Registration Period: Study Approval Date ~ June 30, 2026

(Last Observation Date for Last Patient: ~ December 31, 2026)

Implementation Period (Total Study Period): Study Approval Date ~ March 31, 2030

## **12. Informed Consent Documents and Methods for Obtaining Subject Consent**

The Principal Investigator or Co-Investigator shall provide the research subject with the informed consent document approved by the Kumamoto University Clinical Research Ethics Review Committee (hereinafter referred to as the Ethics Review Committee) and authorized by the head of the research institution. They shall provide a thorough explanation both verbally and in writing and obtain the research subject's written informed consent freely given. Furthermore, when information regarding efficacy, safety, or other factors that could influence the research subject's consent is obtained, or when changes to the implementation plan or other aspects that could affect the research subject's consent are made, the research team shall promptly provide this information to the research subject. The research team shall confirm the research subject's intention regarding participation in the research in advance. The research team shall also revise the explanatory document, etc., after obtaining prior approval from the Ethics Review Committee and permission from the head of the research institution, and obtain renewed consent from the research subject.

